7.2 Molecular Testing Methods

Potential study candidates will undergo molecular testing of tumor tissue or blood in order to first establish eligibility of molecular alterations; those patients with qualifying mutations will then undergo clinical screening, and eligible patients [based on both qualifying mutation(s) and clinical screening] will then be assigned into a patient treatment arm upon confirmation of study eligibility.

Testing of tumor tissue is prioritized over ctDNA for the purpose of determining eligibility for this study. Tumor tissue samples preferred for testing are the most recent tumor sample available; however, testing may be performed on samples taken any time during the disease course. Testing may be performed on primary, recurrent, or metastatic lesions. Biopsies having significant risk should not be performed for the purpose of determining patient eligibility, including but not limited to biopsies of the lung/mediastinum or endoscopic procedures extending beyond the esophagus, stomach, or bowel. However, in the event that a patient desires to consider study participation and no tumor specimen is available, procedures having less risk may be considered.

Tumor tissue or ctDNA may be tested using the Sponsor-provided central laboratory or a Sponsor-approved local laboratory to establish eligibility, with follow-up tissue or ctDNA sample(s) retrospectively analyzed in the Sponsor-provided central laboratory.

Qualifying results by ctDNA testing may be the basis for study eligibility if the search to locate tumor tissue that is suitable for testing shows that none exists.

The analytical techniques employed by the Sponsor-provided central laboratories and criteria for acceptable genetic tumor alterations for this study are described in the Study Laboratory Manual. Included are:

1. Gene panels for the next generation sequencing tests for tumor tissue and ctDNA samples,
2. List of *MET* mutations known to be activating,
3. Description and use of RT-PCR for detection of *MET* exon 14 deletion mutations, and
4. Definitions for quantitative thresholds for positive test results.

If study eligibility is to be based on tumor tissue or ctDNA testing at the Sponsor-provided central laboratory, a 14-day turn-around time should be expected from the time of receipt of adequate samples at the central lab to test results returned to the study site. Questions concerning adequacy of samples will result in delays beyond this timeframe. It is possible that testing could be more rapid, e.g., 8-10 days, but the patient and site should be prepared to wait for confirmation of eligibility for the full duration.

The laboratories employed by the Sponsor to perform initial or retrospective confirmatory evaluation of tumor gene alterations are certified by Clinical Laboratory Improvement Amendments (CLIA). Guidance on sample preparation and submission can be found in the Study Laboratory Manual.

The following laboratories are considered Sponsor-approved local laboratories for this study and prospective confirmation of eligibility from our central laboratory is not required prior to enrollment. Additional Sponsor-approved local laboratories may be added during the study. Tissue and ctDNA samples for retrospective analysis are requested for all patients that are enrolled based on a Sponsor-approved local laboratory test:

- FoundationOne[®], a commercially available next generation gene sequencing test for tumor tissue performed by Foundation Medicine, Inc.
- Caris Molecular Intelligence[®], a commercially available next generation gene sequencing test for tumor tissue performed by Caris Life Sciences.
- Guardant360[®], a commercially available next generation gene sequencing test for ctDNA performed by Guardant Health.

On a case-by-case basis, information in addition to what is typically reported for commercial tests may be needed from Foundation Medicine, Caris Life Sciences and Guardant to make a final determination of eligibility (e.g., quantitative results for gene amplification).

Positive results from a site-specific local laboratory that may meet the criteria for molecular profiling eligibility will need to be confirmed by the Sponsor-provided central laboratory prior to full clinical screening.

7.3 Efficacy

All patients enrolled in the study are to be evaluated for disease activity as outlined in the Schedule of Assessments (Table 2). Disease assessments are to be performed as scheduled according to the calendar days regardless of treatment delays. On-study assessments will be performed at 6 week intervals until approximately 1-year and then every 12 weeks. The allowable windows for assessments are 4 weeks prior to first study treatment for screening/baseline assessments and ± 10 days for on-study disease assessments. CT scans should be performed with contrast agents unless contraindicated for medical reasons. If intravenous contrast is medically contraindicated, the imaging modality to be used (either CT without contrast or MRI) should be the modality which best evaluates the disease, and the choice should be determined by the investigator in conjunction with the local radiologist. Depending on the adequacy for evaluation of disease, a combination of CT without contrast and MRI should most often be used. CT without contrast is preferred for evaluation of lesions in lung parenchyma. MRI is not

adequate for evaluation of lung parenchyma but should also be performed to evaluate all other aspects of the chest. MRI of the abdomen and pelvis should substitute for CT with contrast unless the method does not adequately depict the individual's disease, in which case CT without contrast is preferred.

For patients having effusions or ascites, cytological proof of malignancy should be obtained prior to selection of the effusion as a non-target lesion. Effusions that have not been evaluated using cytology or were found to be non-malignant should not be considered to be cancer lesions.

Screening/baseline tumor assessments should include CT or MRI of the chest and abdomen, pelvis, whole body bone scan, MRI of the brain and evaluation of any superficial lesions. For those sites that routinely use PET scans for assessment of bone lesions in lieu of skeletal scintigraphy, PET scans may be used on-study, with the same modality planned throughout the study for any given patient. CT or MRI of the chest, abdomen, and pelvis will be conducted at every subsequent assessment. Disease assessments subsequent to baseline assessment should also include whole body bone scans and/or MRI of the brain if metastatic disease is identified at screening/baseline by either the investigator OR the central radiology reviewer. Bone scans may be performed at one-half the frequency (every 12 weeks) of other disease assessments. All other suspected sites of disease should be evaluated at each assessment. Disease response will be assessed in accordance with RECIST 1.1 ([Eisenhauer-2009](#)). Appendix 2 provides guidance in using the response criteria and includes a modification to RECIST 1.1 to address potential temporary treatment effects such as tumor lesion cavitation. Assessments will be performed until objective disease progression is documented by the investigator, or subsequent anti-cancer therapy is begun.

Patients experiencing tumor response (Partial Response [PR] or Complete Response [CR]) should undergo confirmatory assessment at least 4 weeks after initial documentation of response. It is acceptable to perform confirmatory assessments at the next appointed evaluation per protocol. Bone scan is required as an element of the assessment of PR or CR response confirmation if bone lesions were identified at the baseline assessment. When bone scans are not protocol-specified, assessment for time point response will be based on assessment of all other lesions with imputation of Non-CR/Non-PD for bone lesions recorded as non-target lesions.

The investigator's assessment of disease response and progression will be the basis for patient management and study expansion decision making. Potential exists for individual tumor lesions to cavitate or become otherwise difficult to evaluate for a period of time as the result of beneficial study treatment impact. For example, tumor necrosis and cavitation may result in minor increase in overall individual lesion size or unclear tumor margins prior to recovery to a smaller lesion, development of scar tissue, or complete resolution. For this reason, investigators may delay reaching the conclusion of disease progression until subsequent on-study disease assessments are performed.

Central radiology review for disease response and progression will be performed in this study and will be the basis for the primary statistical analysis used to estimate the objective response rate and its confidence interval as well as the duration of response and PFS. Materials to be forwarded for independent review will be all imaging studies performed at screening and on study, preferably in digital format, using an electronic transfer through a portal to the review vendor or transfer on compact disc or optical disc. All digital media must be in DICOM format. Films may be forwarded for review if necessary; all films must be originals (second original films acceptable) rather than copies of films. Further information on materials to be forwarded for independent review is provided in the core imaging laboratory Study Manual.

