6.5 Patient Discontinuation/Withdrawal

Patients may discontinue from study treatment or from the study at any time at their own request, or they may be discontinued at any time at the discretion of the investigator or Sponsor for safety, behavioral reasons, or the inability of the patient to comply with the protocol required schedule of study visits or procedures at a given study site.

Criteria that may be used to discontinue patients from receipt of study medication will include, but will not be limited to:

- Objective disease progression according to RECIST 1.1 as determined by the investigator (patients who may derive clinical benefit may continue on treatment at the discretion of the investigator);
- Global deterioration of health status requiring discontinuation;
- Adverse event;
- Significant protocol violation;
- Lost to follow-up;
- Refusal for further treatment;
- Study termination by Sponsor;
- Pregnancy;
- Death.

Reasons for discontinuation from study follow-up may include:

- Study terminated by Sponsor;
- Lost to follow-up;
- Refusal for further follow-up for survival;
- Death.

If a patient does not return for a scheduled visit, every effort should be made to contact the patient. At least 2 attempts should be made to contact the patient, and each attempt should be recorded in the source documents. In any circumstance, every effort should be made to document patient outcome, if possible. The investigator should inquire about the reason for withdrawal, request that the patient returns for a final visit, and if applicable, follow-up with the patient regarding any unresolved adverse events.

If the patient withdraws from the study treatment and also withdraws consent for disclosure of future information, no further evaluations should be performed, and no additional data should be collected. The Sponsor may retain and continue to use any data collected before such refusal for further follow-up.

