9.4 Efficacy Endpoint Definitions and Analyses

9.4.1 Objective Response Rate

Objective disease response will be categorized in accordance with RECIST v1.1 (Appendix 2). Objective Response Rate (ORR) is defined as the percent of patients documented to have a confirmed Complete Response (CR) or Partial Response (PR), as reported by the central review laboratory. The primary analysis will be conducted approximately 12 weeks after the last patient is enrolled, allowing for observation of an early disease response and confirmation of PR or CR. ORR as reported by the investigator in the CRF will be used in secondary and supportive analyses as well as by the Internal Data Monitoring Committee for purpose of decision making using the Bayesian Predictive Probability Design.

Descriptive statistics (frequency and percentage) for ORR, CR, and PR will be presented. The exact 95% confidence interval of these response rates will be constructed. An exact test for single proportion (two-sided $\alpha=5\%$) will be performed to test $H_0: ORR \leq 20\%$ against $H_1: ORR > 20\%$. Other details will be described in the SAP.

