9.4.3 Progression Free Survival

Progression-free survival (PFS) is defined as the time from date of first study treatment to first PD or death due to any cause in the absence of documented PD. Censoring for the PFS endpoint will be assigned on the date of the last tumor assessment if no assessment of tumor progression is identified by the central radiology review and the patient does not die while on study. For patients in whom two or more sequential assessments are missed, followed by the finding of tumor progression, the PFS endpoint will be censored on the date of the last tumor assessment before the gap. Patients lacking an evaluation of disease after first study treatment will have their PFS time censored on the date of first dose with duration of 1 day. Patients who start a new anti-cancer therapy prior to documented PD will have the endpoint censored at the date of the last tumor assessment prior to the start of the new therapy. The Kaplan-Meier method will be used to obtain the estimate of median progression-free survival time.

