9.9 Evaluation of Enrollment Stopping Rules

Disease response and progression as documented by the investigator in the CRF will be the basis for evaluation of the enrollment stopping rules. The following guidelines will apply to each treatment arm when determining number of events in the numerator and denominator in the stopping rules:

1. The numerator will include patients with objective responses (PR or CR) at any time prior to disease progression as assessed by the investigator and documented in the CRF. Unconfirmed responses will be included until sufficient time has elapsed to allow confirmation of response; if the response is not confirmed, the response will be excluded from the numerator during subsequent reviews.
2. The denominator will include:
 - a. Patients included in the numerator;
 - b. Patients discontinued from treatment;
 - c. Patients at the second or subsequent on-study disease assessment (scheduled after 4 treatment cycles, at Week 13) without PR, CR or PD (i.e., patient has Stable Disease [SD] or Not Evaluable [NE]).
3. The denominator will exclude:
 - a. Patients on treatment that have not yet reached the first on-study disease assessment;
 - b. Patients on treatment with SD or NE at the first on-study disease assessment (scheduled after 2 treatment cycles, at Week 7).

At each evaluation of stopping rules, the contribution of each participant's experience to the numerator or denominator will be updated based on current data. For example, a patient having SD at Week 13 may contribute only to the denominator at one evaluation, but be included also in the numerator at the next evaluation based on new data documenting PR or CR at Week 19.

A degree of discordance is expected between investigator assessments of disease response/progression and central review of disease response/progression. No attempt will be made to retrospectively apply the later emerging central review assessments to the enrollment stopping rules.

The IDMC may elect to apply the Bayesian Predictive Probability Design only to those patients taking the SDD formulation in order to mitigate the potential confounding effects from formulation change. These details are outlined in the IDMC charter.

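### Imaging ends at investigator-called progression while PFS and DR are read centrally, so patients with investigator-only progression bias central PFS and DR upward by an amount the documents do not let us fix

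*Combined protocol and SAP*

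**What the plan says.** All places are in the protocol.

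- **When scanning stops (7.3):** "Assessments will be performed until objective disease progression is documented by the investigator, or subsequent anti-cancer therapy is begun". Table 2 and its footnote 12 set the calendar but give no other end point for scanning.
- **Who reads the endpoints (7.3):** central radiology review "will be the basis for the primary statistical analysis used to estimate the objective response rate". The same section applies the central reading to DR and PFS. Section 9.4.1 defines ORR as "the percent of patients documented to have a confirmed Complete Response (CR) or Partial Response (PR), as reported by the central review laboratory".
- **Confirmation (7.3):** responders "should undergo confirmatory assessment at least 4 weeks after initial documentation of response". Appendix 2 reports an unconfirmed PR or CR as SD.
- **Censoring (9.4.3):** "Censoring for the PFS endpoint will be assigned on the date of the last tumor assessment if no assessment of tumor progression is identified". The reading meant is the central one, and the rule applies only if there is no on-study death. Section 9.4.2 has the same rule for DR. PFS, but not DR, also has a stated rule censoring at the last scan before new therapy.
- **Treatment after PD (6.5):** "patients who may derive clinical benefit may continue on treatment at the discretion of the investigator". No matching rule keeps their scans going.
- **Disagreement (9.9):** "A degree of discordance is expected between investigator assessments of disease response/progression and central review of disease response/progression". No rate is given.

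**The concern.** The investigator decides when imaging ends, and a different reader decides whether the endpoint has occurred. When the investigator records PD and central review does not, central follow-up for progression stops at that scan because the patient looked worse. Kaplan-Meier treats a censored patient as having the same prospects as those still at risk, which is implausible here. If the patient later dies on study without new therapy, the PFS event is dated at death, later than central PD would probably have been. Both routes lengthen the estimate.

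Sections 3 and 9.1 contemplate an accelerated-approval application. Durability of response would matter there, and DR and PFS have no comparator arm to offset a shared bias. Scans not taken cannot be restored at analysis.

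**Working it through.** **1. The plan's own figures.** Exact binomial recursion through the Section 9.1 boundaries (0/10 to 13/45) gives type I error 0.0499, power 0.9065, early termination under the null 0.92 and expected size 28.3 (stated 28). All reproduce and none is in dispute. The plan gives no figure for PFS, DR or discordance, so everything in steps 2 to 5 rests on assumptions.

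**2. Size of the PFS bias.** Assumed: investigator PFS exponential with median 6 months, so λ = ln 2/6 = 0.1155 per month; a share d of investigator PDs not PD centrally at that scan; central PD a further exponential delay later, mean δ = 1.4 months (one 6-week interval) to 4.2 months (three intervals).

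- As written, with all discordant patients censored: Kaplan-Meier estimates exp(−λ(1−d)t), with median 6/(1−d).
- Scanning continued to central PD, with μ = 1/δ: S(t) = (1−d)e^(−λt) + d(μe^(−λt) − λe^(−μt))/(μ−λ), solved for S = 0.5.

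| d | As written | Continued, δ=1.4 | Excess | Continued, δ=4.2 | Excess |
|---|---|---|---|---|---|
| 10% | 6.7 | 6.2 | 0.5 | 6.4 | 0.2 |
| 20% | 7.5 | 6.3 | 1.2 | 6.9 | 0.6 |
| 30% | 8.6 | 6.5 | 2.1 | 7.3 | 1.2 |

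(Months; excess taken from unrounded values.) Simulation agrees.

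**3. Deaths counted as events.** Step 2 ignores them. If discordant patients stay at risk until death, the hazard that Kaplan-Meier sees is wλ(1−d) + (1−w)h. Here w is the share of the risk set not yet called PD and h is the death hazard after that call. The excess falls below the table when h > λ(1−d), that is, when median survival after the call is shorter than 6.7, 7.5 or 8.6 months for d = 10%, 20% or 30%. With half the discordant patients counted at death (assumed median 6 months later) and δ = 1.4, simulated excesses are about 0.5, 1.1 and 1.8–1.9. With a 12-month median instead, the excess at d = 20% is about 1.3 rather than 1.2. So the table is a ceiling for short survival after PD and is slightly exceeded for long survival.

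**4. What continued scanning recovers.** Scans would still stop at new therapy. With d = 20% and 50%, 75% or 90% (assumed) of discordant patients switching first:

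- δ = 1.4: the median after the fix is about 6.8, 7.15 or 7.4 months against 7.5 as written. Recovery is about 0.7, 0.4 or 0.15 of the 1.2 months.
- δ = 4.2: recovery is about 0.3, 0.2 or 0.1 of the 0.6 months.

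**5. A second model.** Assumed: 6-weekly visits, true median 18 weeks, investigator PD one visit early in 10%, 20% or 30% of patients, half of those affected switching therapy and the rest counted at death (median 26 weeks later). The 26-week central PFS estimate rises from 0.396 to 0.422, 0.449 and 0.477. The direction is the same.

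**6. Confirmed ORR.** If central PR was first read one visit earlier, the scan called PD is normally about 6 weeks later and can itself confirm. Confirmation is lost when central PR first appears at the scan the investigator calls PD. Each such patient lowers central ORR by 1/45 = 2.2 points. Section 9.4.1 tests central ORR with an exact two-sided 5% test: 14/45 gives p = 0.090 and 15/45 gives p = 0.038. If 5% of true central responders lost confirmation (0.05 × 18 = 0.9 patients at 40% ORR), with futility looks on unaffected investigator reads, the chance of at least 15 central responses falls from 0.851 to 0.782. The 5% is illustrative.

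**The case against.** **Investigator-based results are already planned.** Sections 3 and 9.4.1 use investigator assessments for secondary and supportive analyses, and 9.2 leaves specific censoring rules to the SAP, whose detailed text is not in the combined document. This stands in part: a gap between investigator and central PFS would be visible. It would not show central PFS with only the discordant patients reclassified.

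**Investigators may delay calling PD.** Section 7.3 and Appendix 2 allow this for cavitation, necrosis or flare, which removes one source of discordance. It is optional, covers transient lesion changes only, and lapses once PD is documented.

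**Patients kept on treatment may still be scanned.** A reader might infer from 7.3 that they never are. Table 2 footnote 14 excuses an End of Treatment tumor assessment only if one was done within the previous 6 or 12 weeks, which implies a scan when the last is older. This objection stands: footnote 14 and 7.3 are in tension and must be reconciled.

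**The 13-versus-14 decision.** A reader might infer that a lost central confirmation can flip the 13/45 rule. The documents do not support this. Sections 9.4.1 and 9.9 run the boundaries on investigator reads, and 9.9 rules out applying central reads to them later. Section 9.1 does not name a reader when it declares efficacy above 13 responses, but the specified test of central ORR turns at 14 versus 15.

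**Secondary endpoints.** PFS and DR are single-arm Kaplan-Meier estimates with no planned test. That limits the consequence to how the estimates are read.

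**Conclusion.** The mismatch is real and follows from the text. Central PFS and DR are biased upward whenever investigator-only PD occurs. The direction is well supported; the size is not known. For PFS, under the stated assumptions, the median is overstated by at most about 0.2–2.1 months, provided survival after the investigator's call is no longer than the limits in step 3. These figures scale with the assumed 6-month median. DR has the same mechanism but was not modelled separately.

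The ORR effect is secondary, probably rare and conservative: it can cost power on the central test and does not inflate type I error. Nothing here shows an error in the stated sample size, type I error or power. Nor should a reader infer that continued scanning would remove the whole bias, since patients who switch therapy would still be censored. The change is worth making, but the trial's primary decision does not depend on it.

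**What to change.** 1. **Section 7.3:** continue calendar-based assessments after investigator-only PD until PD is identified by central review, subsequent anti-cancer therapy starts, or consent is withdrawn. State that this includes patients who remain on study treatment under 6.5.
2. **Table 2, footnote 14:** reconcile the End of Treatment tumor assessment with the revised 7.3.
3. **Sections 9.4.2 and 9.4.3:** add a sensitivity analysis that keeps the central reading but counts investigator PD without central PD as an event on that scan date. This also covers patients who switch therapy, whom item 1 cannot help, and goes beyond the investigator-only analysis already planned.

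Cost: protocol wording, and a few additional scans on the existing schedule in patients with investigator-only PD who have not started new therapy. All scans already go to the central reviewer, and central findings already determine on-study brain and bone imaging, so a route from central review to the site exists. The sensitivity analysis needs no new data, and the sample size does not change.

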9.4.2 Duration of Response

Duration of Response (DR) is defined as the time from date of the first documentation of objective tumor response (CR or PR) to the first documentation of Objective Progression of Disease (PD) or to death due to any cause in the absence of documented PD.

Censoring for the DR endpoint will be assigned on the date of the last tumor assessment if no assessment of tumor progression is identified by the central radiology review and the patient does not die while on study. DR will only be calculated for the subgroup of patients with an objective response. The Kaplan-Meier method will be used to obtain the estimate of median DR.

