Potential exists for individual tumor lesions to develop necrosis, to cavitate, have a flair response to treatment or become otherwise difficult to evaluate for a period of time as the result of beneficial study treatment impact. For example, tumor necrosis, cavitation or flair may result in increase in overall size of individual lesions or unclear tumor margins prior to recovery to smaller lesions, development of scar tissue, or complete resolution. The true tumor measurements of lesions should be recorded but the conclusion of progressive disease may be suspended until continued assessment clarifies the nature of the tumor change. If repeat assessments indicate progression of disease, then PD should be recorded on the date of the first assessment giving the impression of progression. If repeat assessments indicate that the change was a process of transition, then NE (not evaluable) should be recorded during the period of transition, and PR or CR may be recorded for subsequent evaluations. The CRF will collect information on the observations during the period of transition to support the assessment conclusions.

Supplemental Investigations

If CR determination depends on a residual lesion that decreased in size but did not disappear completely, it is recommended the residual lesion be investigated with biopsy or fine needle aspirate. If no disease is identified, objective status is CR.

Best Objective Response

Target Lesions	Non-Target Lesions	New Lesion	Point in Time Response	Best Response
CR	CR	No	CR	CR and PR require confirmation at least 4 weeks after first observation
CR	Non-CR/Non-PD	No	PR	
PR	Non-PD	No	PR	
SD	Non-PD	No	SD	SD requires an on-study assessment after at least 6weeks on treatment. Unconfirmed PR or CR are reported as SD.
PD	Any	Yes or No	PD	
Any	PD	Yes or No	PD	
Any	Any	Yes	PD	

Subjective Progression

Patients requiring discontinuation of treatment due to worsening health status attributable to advancement of the malignancy under study but without objective evidence of disease progression should not be reported as PD on tumor assessment CRFs. This should be indicated on the end of treatment CRF as off treatment due to Global Deterioration of Health Status.

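### A suspended progression has no default when no repeat scan follows, so new therapy turns the suspect scan into a PFS censoring: directly in investigator-based analyses, conditionally in the centrally read ones

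*Combined protocol and SAP*

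**What the plan says.** **Suspension.** Section 7.3 allows that "investigators may delay reaching the conclusion of disease progression until subsequent on-study disease assessments are performed". Appendix 2 (Lesion Changes That May Be Transient) says that "the conclusion of progressive disease may be suspended until continued assessment clarifies the nature of the tumor change", without saying who may do this. Measurements are still recorded.

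**Resolution.** Appendix 2 gives two outcomes, both conditional on further scans. The first is: "If repeat assessments indicate progression of disease, then PD should be recorded on the date of the first assessment giving the impression of progression". The second is that the change proves transitional; the interval is then coded not evaluable, and a response may be recorded later. No third outcome is given.

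**End of scanning.** Section 7.3: "Assessments will be performed until objective disease progression is documented by the investigator, or subsequent anti-cancer therapy is begun". Footnote 14 to Table 2 waives the end-of-treatment tumor assessment if one was done within the previous 6 or 12 weeks, according to schedule.

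**PFS (section 9.4.3).** The event is "first PD or death due to any cause in the absence of documented PD". For new therapy: "Patients who start a new anti-cancer therapy prior to documented PD will have the endpoint censored at the date of the last tumor assessment", meaning the last assessment before that therapy.

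**DR (section 9.4.2).** Censoring falls on the last assessment "if no assessment of tumor progression is identified by the central radiology review and the patient does not die while on study". There is no new-therapy rule.

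**Whose reading counts.** Sections 3 and 7.3 base the primary estimates of ORR, DR and PFS on central radiology review. Section 3 uses the investigator's record for secondary and supportive analyses. Section 9.4.1 categorizes response by RECIST 1.1 as set out in Appendix 2 and takes the centrally reported result.

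**The concern.** The suspension rule covers the case where a further scan arrives. It is silent where none does, although other sections make that case foreseeable. A patient whose scan shows growth, whose progression is held open, and who then changes therapy has no documented progression. The date that would have been the event date becomes the censoring date.

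This censoring is unlikely to be independent of outcome. A patient moved to another drug soon after a growing scan is more likely than average to have truly progressed. Kaplan-Meier estimation assumes that censored patients share the prognosis of those still at risk, so PFS would be overstated, and DR among responders likewise. No arm in this study is an untreated or active comparator against which such a bias could cancel.

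**Working it through.** **1. The plan's own figures.** The documents state no assumed median, event count or power for PFS or DR, so there is nothing to reproduce for those endpoints. The stated figures concern ORR. An exact binomial recursion through the 14 stopping boundaries of section 9.1 gives type I error 0.04988 (stated 0.0499), power 0.90652 (stated 0.9065), early termination under the null 0.9199 (stated 0.92) and expected sample size 28.3 (stated 28). These use response counts only, not progression dates or censoring, so this point leaves them unchanged.

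**2. Tracing a patient with a suspended progression and no repeat scan.**

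| What happens next | PFS | DR (if a responder) |
|---|---|---|
| Central reader calls progression on the suspect scan | Event at that scan in the central analysis | Same |
| No progression documented, then new therapy | Censored at the last scan before the therapy, normally the suspect scan | Censored at the last scan unless the patient dies on study; then an event at death |
| No progression documented, no new therapy, death | Event at death, later than the suspect scan | Same |
| Worsening or stopping drug only | No censoring rule triggered; scans should continue | Same |

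The second row carries the problem. In the third, the event is kept but dated late.

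**3. Which analyses are exposed.** Section 3's reference to secondary and supportive analyses is read here as including investigator-based PFS and DR; for these the second row applies directly. For the central analyses it applies only if the central reader may leave the suspect scan unconcluded. Section 7.3 names investigators. Appendix 2 names nobody, and section 9.4.1 ties centrally reported response to Appendix 2. No section settles the matter.

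**4. Illustrative size for PFS.** From the plan: scans every 6 weeks in the first year. Assumed: exponential PFS, true median 5 months, no deaths before progression, and a share f of progressions censored at the scan that showed them.

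- Six weeks = 6 × 12/52 = 1.3846 months.
- Probability of progression per interval: p = 1 − 2^(−1.3846/5) = 0.1747.
- Everyone who progresses leaves the risk set at that scan, but only a share (1 − f) counts. The Kaplan-Meier factor per scan is therefore 1 − (1 − f)p.
- Four scans (to week 24) fall within 6 months and eight (to week 48) within 12 months.

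| f | Factor per scan | 6-month PFS (4th power) | 12-month PFS (8th power) |
|---|---|---|---|
| 0 | 0.8253 | 0.4640 | 0.2153 |
| 5% | 0.8341 | 0.4840 | 0.2342 |
| 10% | 0.8428 | 0.5046 | 0.2546 |
| 20% | 0.8603 | 0.5477 | 0.3000 |

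If 10% of events are instead deaths that still count, simulation gives 6-month values of about 0.46, 0.48, 0.50 and 0.54. Counted events among 45 patients are then 45 × (1 − 0.9f), that is 45, 43, 41 and 37.

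**5. The median.** In continuous time the hazard scales by (1 − f), so the median is multiplied by 1/(1 − f): 1.05, 1.11 or 1.25. On a 6-week grid it moves in steps. At week 24 the curve is at 0.464 for f = 0 and 0.484 for f = 5%, so both medians fall there. For f = 10% and 20% it is still above 0.5 at week 24 and reaches 0.425 and 0.471 at week 30. A small f may therefore leave the reported median unchanged.

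**The case against.** The strongest reply is that the primary DR and PFS analyses are centrally read, that all scans go to the central reader, and that section 7.3 gives the delay to investigators. If the reader calls progression on the suspect scan, it is an event whatever the investigator did. This stands, and it rules out an inference that a reader might draw: that the primary PFS and DR lose these progressions by default. It does not close the gap, because no section says that the reader may not suspend.

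A reader might also infer that any patient who worsens or stops drug after a suspended scan is censored. The documents do not support that. Neither is a censoring trigger, scanning should continue, and death without documented progression is an event. Appendix 2 does say that patients taken off treatment for worsening "without objective evidence of disease progression should not be reported as PD on tumor assessment CRFs", but that clause does not clearly apply where growth was measured. The end-of-treatment waiver makes a missed repeat scan plausible, not required.

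Suspension is also optional, and nothing bars an investigator from concluding progression on the suspect scan. Section 7.3's example is a minor increase or unclear margins, although Appendix 2 sets no limit on size. This bears on how often the problem arises, not on whether a default exists.

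Section 9.2 leaves further censoring rules to the SAP, and no separate SAP text is in the document reviewed, so a rule may exist there. But section 9.2 concerns loss to follow-up and missing observations, whereas this is the classification of a scan already obtained.

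Finally, PFS and DR are secondary and are estimated without a hypothesis test. Section 3 ties the accelerated-approval expansion to ORR precision and the safety database. That limits the consequence.

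**Conclusion.** The point holds in a limited form. Appendix 2 provides no outcome for a suspended progression without a repeat scan. When new therapy comes first, the stated rules make the suspect scan a PFS censoring date. That censoring is probably informative and lengthens PFS. DR is lengthened in the same direction when there is no central progression and no on-study death; a later death counts, but at a later date.

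The effect is direct for investigator-based secondary and supportive analyses, and conditional on the central reader's remit for the primary ones. In the illustration, 6-month PFS rises by about 0.02, 0.04 or 0.08 for f of 5%, 10% or 20%. This rests on an assumed 5-month median, exponential times and an f that the documents do not give. For the central analyses, f requires growth meeting progression criteria, suspension, no later scan and no central progression call, so it may be small. It would be wrong to infer that the ORR design is undermined: its error rates and sample size do not depend on this. The matter should be corrected, but it does not threaten the primary endpoint.

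**What to change.** 1. State in Appendix 2 and section 7.3 whether the central reader may suspend a conclusion of progression or must classify each scan as read.
2. Add to Appendix 2 and sections 9.4.2 and 9.4.3, for analysis only: a scan that meets progression criteria, whose conclusion was suspended and which has no later evaluable scan before new anti-cancer therapy, death or end of follow-up, counts as progression on the date of that scan. Only a repeat scan showing transition reverses it. Report the censored version as a sensitivity analysis, which also covers withdrawals unrelated to disease.
3. Align the new-therapy censoring rules for DR and PFS.

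The cost is a few sentences. Appendix 2 already has the CRF collect observations during the transition period, so the affected scans should be identifiable. The downside is that PFS and DR estimates become slightly shorter, and some transient changes that were never rescanned will be counted as progression. Patient management and the ORR design need no change.
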